## 7.2.2.5. Statistical Analyses / Methods

### 7.2.2.5.1. Statistical Methodology Specification

Endpoint / Variables

 
• Time to first On-treatment moderate/severe HCRU exacerbation
 
• Time to first On-treatment severe HCRU exacerbation
 
• Time to first On-treatment EXACT event
 

Model Specification

 
• Bayesian proportional hazards model
 
• Terms in the model: 
 
○ Response: time to first on-treatment, moderate/severe HCRU exacerbation or EXACT event
 
○ Categorical: treatment group, gender, exacerbation history (<math>\leq 1</math>, <math>\geq 2</math> moderate/severe), smoking status (screening), country
 
○ Continuous: post-bronchodilator % predicted FEV1 (Screening)
 
○ Non-informative priors will be used for all modelling parameters. Wherever possible conjugate priors will be utilised.
 
○ All the terms in the model will follow a normal distribution with a mean of 0 and a SD of 100
 
 
 
• The 'exact' method will be used for handling ties. If the analysis will not run using the 'exact' method, then the 'Efron' method for handling ties will be used instead.
 
• Three chains will be used to calculate the gelman-rubin R statistic: 
 
○ Chain 1: The starting value for all covariates in the model will be the MLE, except dispersion which will be 0.1.
 
○ Chain 2: The starting value for all covariates in the model will be 130% of the MLE, except for dispersion which will be 0.2.
 
○ Chain 3: The starting value for all covariates in the model will be 70% of the MLE, except for dispersion which will be 0.4.
 
 
 
• The seeds used to for the three chains were generated using the ranuni function in SAS and are listed in Section 14.5.2.
 
• Burn-in 2000, thin 5, and 10,000 MCMC samples will be generated for 2000 retained samples
 
• Kaplan-Meier survivor functions will be obtained for each treatment group using PROC LIFETEST with a TIME statement.
 

Model Checking & Diagnostics

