
 
• The proportional hazards assumption will be examined by obtaining the Kaplan-Meier estimates of the survival function <math>S(t)</math> over time separately for each treatment group. In addition, the <math>\ln \{-\ln[S(t)]\}</math> plot will be produced.
 

Model Results Presentation

 
• Hazard ratio and the percent reduction in risk for each danirixin dose compared with placebo with associated 90% CrI.
 
• The probability of having an event, 90% CrI and first quartile and median time to event for each treatment group will be presented.
 
• The probability that the true hazard ratio is less than 1 for each danirixin dose will be presented.
 

- Kaplan-Meier curves showing the probability of having an event over time for each treatment group separately plotted on the same figure

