
 
Actual time will be used for calculation of times to events and Kaplan-Meier plots.
 
Reporting for Data Listings:             
 
Planned and actual time relative to study drug dosing will be shown in listings (Refer to IDSL Statistical Principle 5.05.1).
 
Unscheduled or unplanned readings will be presented within the participant's listings.
 
 
 
									
Unscheduled Visits									

 
Unscheduled visits will not be included in summary tables and/or figures except as part of a maximum/minimum/worst case post-baseline assessment or if they are assigned as the baseline assessment as detailed in Section 5.2.
 
All unscheduled visits will be included in listings.
 
									
Cardiovascular Event Reports									

 
Laboratory results, ECG results/findings and vital signs measurements collected as part of cardiovascular event reports will not be included in any tables, listings or any minimum/maximum post-baseline assessments.
 
									
Time to Event Results									

 
For all time to event analyses, the first quartile and median time to event will be presented. If less than 25% of participants experienced the event within a treatment group then the first quartile will be displayed as NA (not applicable) for that treatment. If less than 50% of participants experienced the event within a treatment group then the median will be displayed as NA for that treatment.
 
									
Descriptive Summary Statistics									
Continuous Data	Refer to IDSL Statistical Principle 6.06.1								
Categorical Data	N, n, frequency, %								
Graphical Displays									

 
Refer to IDSL Statistical Principals 7.01 to 7.13.
 
									
Seeds for Bayesian Analyses									

 
The seeds used to for the Bayesian analyses were generated using the ranuni function in SAS. The same seeds should be applied for all endpoints and populations.
 
									

  
 Chain	Seed	
   
 1	2619	
 
 2	413	
 
 3	9243	
  
		Chain	Seed	1	2619	2	413	3	9243
Chain	Seed								

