
 
The time to first on-treatment Moderate/Severe HCRU exacerbation will be calculated as exacerbation onset date of first on-treatment moderate or severe on-treatment exacerbation – date of start of treatment +1
 
Participants will be represented from their treatment start date to their first on-treatment moderate or severe exacerbation or date of censoring.
 
For the strategic interim analysis, participants that have not experienced an on-treatment exacerbation are censored at the earliest of (treatment stop date + 3, date of death, or the interim cut-off date, 1AUG2018).
 
For the final analysis, participants that have not experienced an on-treatment exacerbation are censored at the earliest of (treatment stop date + 3, date of death, date of exclusion from the per protocol population (if analysis is in Per Protocol population))
 

Raw Annual Rate

 
Raw annual rate is the event rate per 1000 participant-years, calculated as the number of events x 1000, divided by the total duration at risk (minimum(treatment stop date + 1, date of death, date of exclusion from the per protocol population (if analysis is in Per Protocol population)) – treatment start date + 1).
 

Offset Variable

 
For analyses of exacerbation rate, the offset variable will be defined as the logarithm of the ((minimum (date of end of study treatment + 3, date of death, date of exclusion from the per protocol population (if analysis is in Per Protocol population)) – date of start of treatment + 1)/365.25)
 

EXACT Events
General

 
The daily EXACT-PRO scores will be computed according to the EXACT-PRO user manual (Evidera, 2016a) and used to identify EXACT-defined events, including the frequency, duration and severity of the events.
 
Events will be categorized as recovered, censored, or persistent worsening (according to the manual).
 

Time to First Event

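### As worded, the SAP shows the first quartile or median time to event as NA on the crude event percentage, so a quartile that the Kaplan-Meier curve supplies can be blanked

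*SAP*

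**What the plan says.** The display rule is in SAP 14.5.2, under Time to Event Results. Its scope is general: "For all time to event analyses, the first quartile and median time to event will be presented". For the first quartile it says "If less than 25% of participants experienced the event within a treatment group then the first quartile will be displayed as NA", and for the median "If less than 50% of participants experienced the event within a treatment group then the median will be displayed as NA for that treatment".

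The method is in SAP 7.2.2.5.1, which covers time to first moderate/severe HCRU exacerbation, first severe HCRU exacerbation and first EXACT event: "Kaplan-Meier survivor functions will be obtained for each treatment group using PROC LIFETEST with a TIME statement". The results paragraph of that section lists what is shown by arm: "The probability of having an event, 90% CrI and first quartile and median time to event for each treatment group will be presented".

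SAP 14.6.3 defines censoring. For HCRU exacerbations, "participants that have not experienced an on-treatment exacerbation are censored at the earliest of (treatment stop date + 3, date of death", with the date of per-protocol exclusion added for the final analysis and the data cut-off for the strategic interim. For EXACT events, the last diary assessment and the day before treatment stop also censor. No section restates the 25% or 50% in 14.5.2 as a Kaplan-Meier percentage.

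**The concern.** The rule and the estimator use different quantities. A Kaplan-Meier quartile is the time at which the estimated cumulative risk passes 25% among those still under observation. The rule instead asks whether 25% of everyone in the arm was seen to have the event. Someone censored in week 3 counts fully in the denominator of the crude share but leaves the Kaplan-Meier risk set.

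An arm whose curve crosses 25% can thus have a first quartile on its plot and NA in its table. The gap between the two percentages grows with early censoring, so two arms with the same curve could show a time in one column and NA in the other only because one had more discontinuations. Time to first HCRU exacerbation is listed among the key secondary endpoints in the Protocol synopsis, and the arms will be read side by side in a dose-ranging study, so a difference of that kind could be misread.

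**Working it through.** The SAP gives no figure here to reproduce; the check is of the rule against the estimator.

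**Inputs from the documents**
- Arm size: about 600 randomised equally to six arms (Protocol 5.2 and 10.3), so 600 / 6 = 100.
- Dropout: about 10% (Protocol 5.2). Check: 600 x (1 - 0.10) = 540, the stated number of completers.
- Follow-up: 168 days, plus the 3-day window for HCRU events, giving 171.

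**Assumptions**
- The 24-week event risk *p*. The documents give none, so a range is shown.
- The share *c* censored early. Only the 10% dropout is documented; other values are illustrations.
- Exponential event times, with early censoring spread uniformly over 171 days.

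**Step 1: direction.** With *n* in the arm and *d* events, the crude share is *d/n*. In Kaplan-Meier, the weight of each censored participant passes to those still at risk, so every event carries a weight of at least 1/*n* and

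1 - S(end) >= *d/n*,

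with equality only when nobody is censored before an event. The crude rule can therefore hide an estimable quartile, but it cannot let a non-estimable one through.

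**Step 2: worked example.** Take 100 in the arm, 10 censored before the first event, and 24 events among the other 90, who are followed to the end. Crude share: 24/100 = 24%, shown as NA. Kaplan-Meier: 24/90 = 26.7%, so the first quartile exists. With 20 censored early and 22 events among 80, the figures are 22% and 22/80 = 27.5%.

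**Step 3: width of the gap.** Under the assumptions, the expected crude share is

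(1 - *c*) x *p* + *c* x [1 - *p* / (-ln(1 - *p*))].

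At *p* = 0.25 and *c* = 0.10: 0.9 x 0.25 + 0.1 x (1 - 0.25/0.2877) = 0.225 + 0.013 = 0.238. Solving for the risk at which the crude share reaches the threshold:

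| Early censoring | Risk needed for crude 25% | Risk needed for crude 50% |
|---|---|---|
| 5% | 25.6% | 51.1% |
| 10% | 26.2% | 52.3% |
| 20% | 27.6% | 54.8% |
| 30% | 29.1% | 57.4% |

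The band in which a quartile is lost is narrow at the planned dropout and widens with censoring.

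**Step 4: how often.** Simulation of 20,000 arms of 100 per setting, counting arms where the Kaplan-Meier estimate passes the threshold and the crude share does not. Kaplan-Meier was below crude in no arm.

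| True 24-week risk | First quartile wrongly NA, 10% censored | 20% censored |
|---|---|---|
| 15% | 0.2% | 0.6% |
| 20% | 3% | 7% |
| 25% | 6-7% | 17% |
| 30% | 4% | 12-13% |
| 35% | 0.9% | 3.6% |
| 37% | 0.4% | 1.8% |
| 40% | 0.1% | 0.4% |

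For the median at 10% censoring, the rate is about 7% at 45% risk, 13% at 50%, 10% at 55% and 3% at 60%.

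**The case against.** **The sentence may only be loose wording.** It sits in a display-standards appendix, the method section names PROC LIFETEST, and the phrase could be shorthand for a curve that does not reach 25%. That is possible, and nothing shows that the author meant a programmer to overwrite an estimate. But the text as written is a count of participants, it applies to every time-to-event analysis, and no other section corrects it. Someone programming from it would be right to apply the crude count. The point is therefore about the rule as worded.

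**A reader might infer that, with six arms and three endpoints, at least one wrong NA is likely.** The documents do not support that. At 10% early censoring and a per-arm rate of 4-7%, the chance over six independent arms of one endpoint is 1 - (1 - 0.04)^6 = 22% to 1 - (1 - 0.07)^6 = 35%, and that already needs every arm near 25% risk. Carrying it to 18 arm-by-endpoint cells would need all three endpoints near 25%. Severe exacerbations are a subset of moderate/severe ones, so this is implausible and the cells are not independent. At 20% censoring the six-arm figure is about 1 - (1 - 0.17)^6 = 67%, but no document gives 20%. Moreover, several per-protocol criteria in SAP 14.1.1 (the eligibility failures, and prohibited drugs taken before randomisation) remove the participant altogether and create no mid-study censoring.

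**The risk may lie elsewhere.** Eligibility requires two or more exacerbations in the prior year, or one with raised fibrinogen (Protocol 6.1). If the on-study rate were 1 per year (an assumption), the 24-week risk would be about 37%, where the first-quartile effect is under 0.5%. This stands as a limit on the size.

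**Nothing important is hidden.** Kaplan-Meier plots are planned for all three endpoints (SAP 14.11.6, final Figures 2.16, 2.17 and 2.19), and the hazard ratio is the summary measure (SAP 7.2.2.2). This also stands: a suppressed quartile can be read off the plot.

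**Conclusion.** The point holds as a minor one. The rule in SAP 14.5.2, taken as written, can put NA where the Kaplan-Meier curve gives a first quartile or median. The error goes in one direction only, and for equal risk it is more frequent in arms with more early censoring.

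Its size depends on an event risk that the documents do not state. With 100 per arm and 10% censored early, about 3-7% of arms are affected at a 24-week risk of 20-30%, and under 0.5% at 37% or more; the median is affected only near 50%. Per-protocol arms may be smaller than 100, and per-protocol or diary censoring may add to the 10%, but by how much is unknown.

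It would be wrong to read this as a bias in the treatment comparison. The hazard ratios, their credible intervals, the plots and the primary endpoint do not use the rule. What is at stake is agreement between a descriptive table and its own Kaplan-Meier figure.

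**What to change.** Replace the two NA sentences in SAP 14.5.2 with one: *The first quartile (median) will be displayed when the Kaplan-Meier estimate of the event probability for the arm reaches 25% (50%) during follow-up, and as NA otherwise.*

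This loses no protection, because an arm whose curve never reaches the threshold is still NA. It needs no new data and no new analysis, since SAP 7.2.2.5.1 already obtains the survivor functions for each arm. The SAP describes the strategic interim as already performed, so the change would apply to the final tables.

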### 14.5.3. Reporting Standards for Pharmacokinetic Data

Pharmacokinetic Concentration Data	
PC Windows Non-Linear (WNL) File	PC WNL file (CSV format) for the non-compartmental analysis by Clinical Pharmacology Modelling and Simulation function will be created according to GUI_51487 and PKOne documents. Note: Concentration values will be imputed as per GUI_51487
Descriptive Summary Statistics, Graphical Displays and Listings	Refer to IDSL PK Display Standards. Refer to IDSL Statistical Principle 6.06.1. Note: Concentration values will be imputed as per GUI_51487 for descriptive summary statistics/analysis and summarized graphical displays only. Additionally , include geometric mean and 90% CI for the summary of blood concentration data.
NONMEM/Pop PK File	PopPK file (CSV format) for the PopPK analysis by Clinical Pharmacology Modelling and Simulation function will be created according to the data specification detailed in Appendix 9 .
Pharmacokinetic Parameter Derivation	
PK Parameter to be Derived by Programmer	None
Pharmacokinetic Parameter Data	
Is NQ impacted PK Parameters Rule Being Followed	No.
Descriptive Summary Statistics, Graphical Displays and Listings	Refer to IDSL PK Display Standards.

## 14.6. Appendix 6: Derived and Transformed Data

### 14.6.1. General

Multiple Measurements at One Analysis Time Point

 
• Mean of the measurements will be calculated and used in any derivation of summary statistics but if listed, all data will be presented.
 
• Participants having both High and Low values for Potential Clinical Importance criteria at any post-baseline visit for safety parameters will be counted in both the High and Low categories of “Worst case post-baseline” row of related summary tables.
 

Study Day

 
• Calculated as the number of days from First Dose Date: 
 
• Ref Date = Missing → Study Day = Missing
 
• Ref Date < First Dose Date → Study Day = Ref Date – First Dose Date
 
• Ref Date ≥ First Dose Date → Study Day = Ref Date – (First Dose Date) + 1
 
 
 

Study Treatment Stop Date

 
• If the study treatment stop date is missing, it will be imputed as follows: 
 
• If any of EW Visit date, Visit 10 (Day 168) date or date of death are non-missing then the study treatment stop date will be imputed as the minimum of (EW Visit date, Visit 10 (Day 168) date, date of death, date that all study treatment containers were returned).
 
• For all other missing treatment stop dates, the last recorded exposure start or stop date will be used.
 
 
 
• For ongoing participants at the strategic interim, treatment stop date will be imputed as 5SEP2018
 

Study Completion Definition

 
• A participant is considered to have completed the study if they have not withdrawn and attended Visit 10.
 

### 14.6.2. Study Population

Demographics
Age

 
• GSK standard IDSL algorithms will be used for calculating age where birth date will be imputed as follows: 
 
○ Any participant with a missing day will have this imputed as day ‘15’.
 
○ Any participant with a missing date and month will have this imputed as ‘30th June’.
 
 
 
• Birth date will be presented in listings as ‘YYYY’.
 
• Age will be calculated based on the Pre-screening visit date.
 
• Age group categories are 18-64, 65-74, 75-84, >=85
 

Body Mass Index (BMI)

 
• Calculated as Weight (kg) / [Height (m)]
 

Baseline Characteristics
% Predicted Normal FEV1 at Screening

 
The following categories will be derived: <50%, >=50%
 

Smoking Status

 
If the last smoked date (SUSMLSDT) is missing and a partial date (SUSMLSD) is not missing, then the following imputation should be applied to the partial smoking date for use in the reclassification of smoking status calculation: 
 
'01' will be used for the day and 'Jan' will be used for the month.
 
 
 
Former smokers will be reclassified as current smokers if screening date – last smoked date < 183 days.
 

Chronic Mucus Hypersecretion

 
A participant is considered to have CMH (CMH+) if baseline SGRQ Q1(cough) = Most or several days a week AND baseline SGRQ Q2 (phlegm) = Most or several days a week.
 
A participant is considered not to have CMH (CMH-) if baseline SGRQ Q1(cough) not equal to Most or several days a week OR baseline SGRQ Q2(phlegm) not equal to Most or several days a week and both questions are non-missing at baseline.
 
Otherwise participants are considered to have a missing CMH status.
 

Baseline E-RS: COPD Total Score Categories

 
The following categories will be derived for baseline E-RS: COPD Total Score 
 
<8, >=8
 
<10, >=10
 
<12, >=12
 
 
 

Exacerbation History Categories

 
Exacerbations (historical) will be classified as follows: 
 
Mild: Managed without oral/systemic corticosteroids and/or antibiotics (not involving hospitalisation)
 
Moderate: Requiring oral/systemic corticosteroids and/or antibiotics (not involving hospitalisation)
 
Severe: Requiring hospitalisation
 
Moderate/severe: Requiring oral/systemic corticosteroids and/or antibiotics or hospitalisation.
 
 
 
The total number of moderate/severe exacerbations will be categorized as ≤1, ≥2 for inclusion as a covariate in statistical models.
 

GOLD Grade 1-4 at Screening

 
Participants will be classified into Global Initiative on Obstructive Lung Disease (GOLD) Grades 1-4 using the post-bronchodilator percent predicted FEV1 assessment at Screening: 
 
GOLD Grade 1 (Mild): percent predicted FEV1 ≥80%
 
GOLD Grade 2 (Moderate): 50%≤ percent predicted FEV1 <80%
 
GOLD Grade 3 (Severe): 30%≤ percent predicted FEV1 <50%
 
GOLD Grade 4 (Very Severe): percent predicted FEV1 <30%
 
 
 

GOLD Grade A-D at Screening

 
Participants will be classified into GOLD Grades A-D definitions as follows: 
 
A. Low risk, less symptoms: baseline CAT < 10 AND GOLD Grade 1-2 AND ≤1 exacerbation; (no hospitalizations for exacerbations), prior year.
 
B. Low risk, more symptoms: baseline CAT >= 10 AND GOLD Grade 1-2 AND ≤1 exacerbation (no hospitalizations for exacerbations), prior year
 
C. High risk, less symptoms: baseline CAT < 10 AND either GOLD Grade 3-4 OR ≥ 2 exacerbations, prior year OR >=1 exacerbation leading to hospitalization, prior year
 
D. High risk, more symptoms: baseline CAT >= 10 AND either GOLD Grade 3-4 OR ≥ 2 exacerbations, prior year OR >=1 exacerbation leading to hospitalization, prior year
 
 
 

Baseline Characteristics
Participant Disposition

 
• For Kaplan-Meier plots of study withdrawal over time, censoring will be performed as follows: 
 
○ Participants are represented from their Day 1 date to the date of early withdrawal from the study (or date of death). Participants that completed the study are censored at the earliest of the date of completion and Day 168.
 
 
 

Medical Conditions and Concomitant Medications
Respiratory Medication Class

 
• COPD concomitant medications will be grouped into the following RMCs based on pre-defined code lists derived from ATC classifications: 
 
○ Androgens and Estrogens
 
○ Anti-IgE, Anti-IL5
 
○ Anticholinergic
 
○ Antiinfectives (antibiotics, antiseptics only)
 
○ Antimycotics
 
○ Antivirals
 
○ Beta 2 Agonist
 
○ Corticosteroid – Inhaled
 
○ Corticosteroid – Depot
 
○ Corticosteroid – Systemic, oral, parenteral and intra-articular
 
○ Corticosteroid – Other
 
○ Leukotriene Receptor Antagonist
 
○ Long-acting anticholinergic
 
○ Long-acting beta-2 agonist
 
○ Mucolytics
 
○ Nedocromil or Cromolyn Sodium
 
○ Oxygen
 
○ PDE4 Inhibitors
 
○ Short-acting anticholinergic
 
○ Short-acting beta-2 agonist
 
○ Xanthine
 
○ Other medication given for exacerbation
 
○ Other COPD medication
 
 
 

COPD Medication Combination

 
• COPD medications will be summarized at the following time points: 
 
○ At Screening: Taken on the day of the Screening visit excluding medications that stopped on the day of the Screening visit
 
○ At Baseline: Taken on the day of start of treatment
 
○ At Month 6: Taken during Month 6 (Study Day 141 to earliest of (Study day 168 and day before study treatment stop date))
 
 
 
• Medication combinations of all RMC categories will be derived. Medications will be summarized based on individual and combinations of the following RMC categories, with or without other medications: 
 
○ ICS
 
○ LABA
 
○ LAMA
 
○ Xanthine
 
○ PDE4 inhibitor
 
○ Anti-IgE, Anti-IL5
 
 
 

Medical Conditions and Concomitant Medications
Cardiovascular Risk Factors

 
• Subjects with at least one of the following current or past medical conditions at Screening will be classed as having cardiovascular (CV) risk factor at screening. The number of CV risk factors at Screening (0, 1, or >=2) will be derived.                             
 
○ Coronary artery disease
 
○ Myocardial infarction
 
○ Arrhythmia
 
○ Congestive heart failure
 
○ Hypertension
 
○ Cerebrovascular accident
 
○ Hypercholesterolemia
 
○ Diabetes mellitus
 
 
 

Compliance
Treatment Compliance

Compliance= (tablets issued–tablets returned) x 100 / 2 x (treatment stop date – treatment start date +1)
 
If any count of tablets returned is missing overall compliance will be set to missing.
 
 
• Compliance will be categorized as follows:                             
 
< 80 %
 
≥ 80 % to < 95 %
 
≥ 95 % to ≤105 %
 
>105 % to ≤120 %
 
>120 %
 
 
 
• If a participant received a treatment other than the randomized treatment during the study, the compliance will still be calculated using data from all containers received and overall treatment start and stop dates.
 

Daily Diary Compliance

Overall compliance= (number of days with non-missing data between study treatment start and the earliest of (Study day 168 and day before study treatment stop)) x 100 / (Earliest of (Study day 168 and day before study treatment stop date) – treatment start date +1)
 
 
• Overall compliance will be categorized as follows:                             
 
< 50 %
 
≥ 50 % to < 60 %
 
≥ 60 % to < 70 %
 
≥ 70 % to < 80 %
 
≥ 80 % to < 90 %
 
≥ 90 % to ≤100 %
 
 
 
 
Baseline and Monthly compliance= number of days with non-missing data between periods defined in Section 14.6.3
 
 
• Baseline compliance will be categorized as follows: Number of days completed <4, ≥4
 
• Monthly compliance will be categorized as follows: Number of days completed <10, 10-20, >20
 

Exposure
Exposure to Study Treatment
Duration of exposure to study treatment is calculated as (treatment stop date – treatment start date +1).
The following exposure categories will be derived: ≥1 day, ≥4 weeks, ≥8 weeks, ≥12 weeks, ≥16 weeks, ≥20 weeks and ≥24 weeks. An additional category of 23-25 weeks will also be summarized.

